8.6 Relapse-free survival (RFS)

- Time from date of response until the date of first objective documentation of disease-relapse.

8.7 Overall survival (OS)

- Time from date of treatment start until date of death due to any cause.

9.0 Criteria for Removal from the Study

Patients are free to withdraw consent and discontinue participation in the study at any time and without prejudice to further treatment. Patients may be discontinued from the study for the following reasons:

1. Patient requests discontinuation.
2. There is unacceptable toxicity (i.e., NCI CTCAE version 4 grade 4 drug-related non hematologic toxicity).
3. Patient experiences an NCI CTCAE version 4 \geq grade 3 drug-related non-hematologic toxicity or clinically significant infection of any grade that is not recovered by Day 75 from the onset of the toxicity.
4. Patient experiences a third occurrence of an NCI CTCAE version 4 grade 3 drug-related non-hematologic toxicity.
5. Patient experiences asymptomatic grade 2 total bilirubin or creatinine abnormality that is not recovered by Day 75 from the onset of the toxicity.
6. There is a need for any treatment not allowed by the protocol.
7. Treatment failure or disease relapse.
8. Investigator discretion.

10.0. Regulatory and Reporting Requirements

Adverse event reporting will be as per the NCI criteria and the MDACC Leukemia Specific Adverse Event Recording and Reporting Guidelines.

The descriptions and grading scales found in the revised NCI Common Terminology Criteria for Adverse Events (CTCAE) most current version will be utilized for adverse event reporting. (<http://ctep.cancer.gov/reporting/ctc.html>).

10.1 Expedited adverse event reporting

Refer to **Appendix C** for Leukemia-Specific Adverse Event Recording and Reporting Guidelines.

These guidelines serve to bring the Department of Leukemia in compliance with the institutional policy on Reporting of Serious Adverse Events-definition of expected AE-

"All clinical protocols should include a list of the expected and anticipated events or hospitalizations relating to the study treatment" and Guideline for Good Clinical Practice 4.11.1 "All serious adverse events (SAEs) should be reported.

Adverse event is any untoward medical occurrence that may present during treatment with a pharmaceutical product but which does not necessarily have a causal relationship with this treatment.

Adverse drug reaction is a response to a drug which is noxious and unintended and which occurs at doses normally used in man for prophylaxis, diagnosis, or therapy of disease or for the modification of physiologic function.

Assessing causal connections between agents and disease is fundamental to the understanding of adverse drug reactions. In general, a drug may be considered a contributory cause of an adverse event if, had the drug not been administered, 1) the event would not have happened at all, 2) the event would have occurred later than it actually did, or 3) the event would have been less severe.

Adverse Events (AEs) will be evaluated according to current CTC version in each protocol.

Expected events during leukemia therapy are:

1. *Myelosuppression related events (due to disease or leukemia therapy)*
 - a. *febrile or infection episodes not requiring management in the intensive care unit*
 - b. *epistaxis or bleeding except for catastrophic CNS or pulmonary hemorrhage*
 - c. *anemia, neutropenia, lymphopenia, thrombocytopenia, leukopenia, leukocytosis*
2. *Disease related events*
 - a. *symptoms associated with anemia*

- i. *fatigue*
 - ii. *weakness*
 - iii. *shortness of breath*
 - b. *electrolyte abnormalities (sodium, potassium, bicarbonate, CO₂, magnesium)*
 - c. *chemistry abnormalities (LDH, phosphorus, calcium, BUN, protein, albumin, uric acid, alkaline phosphatase, glucose)*
 - d. *coagulation abnormalities*
 - e. *disease specific therapy (induction, maintenance, salvage, or stem cell therapy)*
 - f. *alopecia*
 - g. *bone, joint, or muscle pain*
 - h. *liver function test abnormalities associated with infection or disease progression*
 - i. *disease progression*
- 3. *General therapy related events*
 - a. *catheter related events*
 - b. *renal failure related to tumor lysis syndrome or antibiotic/antifungal therapy*
 - c. *rash related to antibiotic use*
- 4. ***Hospitalization for the management of any of the above expected events***

11.0 Statistical Considerations

The proposed study is a single-arm phase II clinical trial study in patients with MDS who have failed therapy with hypomethylating agents. The primary endpoint is to determine the overall survival, defined as the time from treatment start to the time of death. A maximum of 80 patients will be accrued at a rate of 1 to 5 patients per month (maximum accrual period 3.33 years). Additional 12 months of follow-up is planned after the last patient is accrued into the trial. It is anticipated that treatment with OM will prolong the

median OS from 4.2 months, as shown in the current standard therapy, to 6 months. The CR, overall survival and toxicity will be monitored during the study, and all data will be used to update the prior distributions for toxicity and efficacy parameters. It will be postulated that the treatment can achieve a CR rate of 20 percent.

We compare median survival time among patients in this study to historical median survival time of 4.2 months. We assume an exponential distribution of failure in the study group and a two-sided significance level of 0.05. Given one additional year of follow up after study recruitment and an accrual rate of 1-5 patients per month, 80 patients will yield a power of 84% to test for a 1.8 months improvement in median survival from 4.2 months.

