11.1 Overall Survival Monitoring

The efficacy endpoint, OS, will be continuously monitored using the Bayesian method by Thall et al.³⁷ Let T_s and T_e represent the OS times for the historical regimen and the experimental regimen OM, respectively. We assume $T_s|M_s$ and $T_e|M_e$ follow an exponential distribution with respective median M_s and M_e . Furthermore, we assume that the prior for M_s follows an inverse gamma distribution $IG(5.0, 16.8)$ to reflect our knowledge of OS in patients treated historically with standard regimen. This prior distribution has a mean of 4.2 months, and a variance of 5.88. The prior for M_e is assumed to be $IG(2.18, 4.94)$, which has the same mean of 4.2 months and a larger variance of 100 to reflect our uncertainty about the median OS of the proposed experimental regimen, OM.

The OS will be continuously monitored, and the study will be terminated early if, based on the available data, there is less than 5% chance that the median OS in patients treated with OM will improve by more than 1.8 months, compared to the historical regimen. The futility stopping rule is as follows:

$$\Pr(\text{Me} > \text{Ms} + 1.8 \text{ months} \mid \text{data}) < 0.05$$

The operating characteristics of this decision rule are summarized in Table 1 using the one-arm TTE software developed by the Department of Biostatistics at M.D. Anderson Cancer Center.

Table 1. Operating characteristics for the design (based on 5000 simulations)

Scenario	True Median (months)	$\Pr(\text{Stopped Early})$	Mean No. patients	Average Trial Duration (months)
1	2.0	0.9999	13	16.26
2	3.0	0.8882	32	22.54
3	4.2	0.2332	66	34.00
4	5.0	0.1088	73	36.29
5	6.0	0.0478	77	37.58
6	7.0	0.0236	78	38.05

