The monitoring for OS will be carried out through the Clinical Trial Conduct (CTC) website (<https://biostatistics.mdanderson.org/ClinicalTrialConduct>) which is housed on a secure server at MDACC and maintained by the MDACC Department of Biostatistics. Access to the website will be gained through usernames and passwords provided by the MDACC Department of Biostatistics. Training on the use of the CTC will be provided by the biostatistical collaborator of the study, with emphasis on the importance of timely updating of follow-up times and recording of events. The monitoring rule for OS will be applied continuously when a new patient is enrolled or an existing patient's data is updated. If the stopping rule is met, an automatic email will be sent out to the study PI, RN and the study statistician to keep them informed and the CTC website will not allow enrollment of any new patients.

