11.2. CR Rate and Toxicity Monitoring

Complete response rate and toxicity will be monitored simultaneously using the Bayesian approach of Thall, Simon, Estey (1995, 1996) and the extension by Thall and Sung (1998). This regimen of the experimental treatment will be considered worthy of further investigation if it elicits an increase in CRR to 20% with acceptable toxicity. A toxicity rate greater than 30% is considered unacceptable. Thus, a beta (20, 80) and beta (0.4, 1.6) priors were assumed for the standard treatment response distribution and experimental treatment response prior distribution, respectively. In addition, a beta (30, 70) and beta (0.6, 1.4) priors were assumed for the standard treatment toxicity rate and experimental treatment toxicity prior distribution, respectively. Interim monitoring rules, assuming the prior distributions, were constructed that meet the following two conditions,

- 1) $\Pr(\theta_{S, \text{Toxicity}} < \theta_{E, \text{Toxicity}} | \text{data}) > 0.975$ and,
- 2) $\Pr(\theta_{E, \text{CR}} > \theta_{S, \text{CR}} | \text{data}) < 0.025$

Where $\theta_{E, \text{Toxicity}}$ and $\theta_{E, \text{CRR}}$ are the toxicity and response rates for the experimental treatment, and $\theta_{S, \text{Toxicity}}$ and $\theta_{S, \text{CRR}}$ are the toxicity and response rates for the standard treatment respectively. The first rule provides for stopping the study if excessive toxicity is highly probable (i.e., probability >97.5%) for the experimental treatment. The second condition will stop the study early if the data suggest that it is unlikely (i.e., probability < 2.5%) that CR rate of the experimental treatment is 20%. Assuming the minimum number of patients is 5, the maximum number of patients is 80 and the cohort size is 5. Multc Lean Desktop (version 2.1.0) was used to generate the toxicity and futility stopping boundaries and the OC table (Table 4). The monitoring rule for the toxicity rate, based on these assumptions and monitoring conditions above is in Table 2. Toxicity is defined as grade 3 or higher drug-related non-hematologic toxicity during the first cycle. For example, accrual will cease if 5 patients experience toxicities among the first 5 patients treated or if 7 or more patients experience toxicities among the first 10 patients.

Table 2. Stop accrual if the number of toxicities is greater than or equal to indicated (i.e., # patients with toxicities) among the number of patients evaluated

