# patients evaluated	# patients with toxicities	# patients evaluated	# patients with toxicities
5	5	45	22-45
10	7-10	50	24-50
15	9-15	55	26-55
20	11-20	60	28-60
25	14-25	65	30-65
30	16-30	70	32-70
35	18-35	75	34-78
40	20-40	80	Always stop with his many patients

Monitoring the response rate, based on the above assumptions will begin after 5 patients are treated, on an intent-to-treat basis (Table 3). For example, accrual will cease if 0 patients experience a response in the first 10 patients treated.

Table 3. Stop accrual if the number with CR is less than or equal to indicated (i.e., # patients with CR) among the number of patients evaluated							
# patients evaluated	10-20	25-30	35-40	45	50-55	60-65	70
# patients with CR	0	0-1	0-2	0-3	0-4	0-5	0-6

The probability of stopping the study early for low CRRs (i.e., 10%) was higher than 0.70 when toxicity rates were ranged from 20% to 40%. Probabilities of stopping early for high true toxicity rates (i.e., 40%) were 81% when the true CR rate was 10% and 45% when true CRR was 20%.

Table 4. Operating characteristics for simultaneous monitoring response and toxicity rates for patients treated				
True CRR	True Toxicity Rate	True Probability Vector (CRR/Tox, CRR/NoTox, NoCRR/Tox, NoCRR/NoTox)	Probability of Stopping	Average number of patients treated
10%	20%	(0.02, 0.08, 0.18, 0.72)	0.6960	44
10%	30%	(0.03, 0.07, 0.27, 0.63)	0.7076	43
10%	40%	(0.04, 0.06, 0.36, 0.54)	0.8054	36
20%	20%	(0.04, 0.16, 0.16, 0.64)	0.1346	71
20%	30%	(0.06, 0.14, 0.24, 0.56)	0.1676	69
20%	40%	(0.08, 0.12, 0.32, 0.48)	0.4462	57

30%	20%	(0.06, 0.24, 0.14, 0.56)	0.0309	78
30%	30%	(0.09, 0.21, 0.21, 0.49)	0.0679	76
30%	40%	(0.12, 0.18, 0.28, 0.42)	0.3798	61

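### The 84% power for overall survival holds only if all 80 patients are enrolled; with the plan's three stopping rules in force it is about 67–74%

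*Combined protocol and SAP*

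**What the plan says.** Section 11.0 sizes the trial on OS. It assumes exponential survival, a historical median of 4.2 months, a two-sided 0.05 level and one further year of follow-up, and concludes that "80 patients will yield a power of 84% to test for a 1.8 months improvement in median survival from 4.2 months". The same section treats 80 as a ceiling: "A maximum of 80 patients will be accrued at a rate of 1 to 5 patients per month (maximum accrual period 3.33 years". It also sets a response target: "It will be postulated that the treatment can achieve a CR rate of 20 percent".

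Three rules can end enrolment before 80:

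- **OS futility (section 11.1).** "The OS will be continuously monitored, and the study will be terminated early if" the posterior chance of a gain above 1.8 months falls below 5%. Once the rule is met, "the CTC website will not allow enrollment of any new patients".
- **Toxicity (section 11.2, Table 2).** "A toxicity rate greater than 30% is considered unacceptable", and for example "accrual will cease if 5 patients experience toxicities among the first 5 patients treated".
- **Low CR (section 11.2, Table 3).** For example, "accrual will cease if 0 patients experience a response in the first 10 patients treated".

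Table 1 gives the operating characteristics of the OS rule alone. Table 4 gives those of the CR and toxicity rules together. No section combines either table with the 84%, and none says whether the OS comparison is carried out on the enrolled patients after an early stop.

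**The concern.** A power statement should describe the design that will be run. Here the sample-size figure is for a fixed sample of 80, while the trial is monitored by three rules that sometimes stop it even when the drug performs exactly as postulated. The loss cannot be read from any one table, because the OS rule and the CR/toxicity rules are reported separately.

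OS is the endpoint on which the trial was sized. A reader of section 11.0 will expect a 16% chance of missing a true gain from 4.2 to 6 months. If the real figure is nearer 30%, a negative or truncated trial is weaker evidence against the drug than the plan suggests. This is not a criticism of having the rules, only of the power figure placed beside them.

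**Working it through.** **Inputs.** From section 11.0: medians 4.2 and 6.0 months, exponential survival, two-sided 0.05, up to 80 patients at 1–5 per month, 12 months of further follow-up, CR 20%. From Table 1: stopping probability 0.0478 at median 6. From Table 4 at CR 20%: stopping probability 0.1346 (toxicity 20%) and 0.1676 (toxicity 30%). The plan states no expected toxicity rate, so these two rows are used as scenarios; 30% is the acceptability limit. Table 1 implies accrual of 3 per month: 77 / (37.58 − 12) = 3.01.

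**Step 1: reproduce the 84%.** The hazards are ln 2/4.2 = 0.165 and ln 2/6 = 0.1155, a ratio of 0.70. With uniform accrual over A months, expected deaths are 80 × [1 − e^(−12λ)(1 − e^(−Aλ))/(Aλ)]. At 3 per month A = 26.7, which gives d₁ = 73.8 under the alternative and d₀ = 77.5 under the null.

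- Log scale: Φ(√73.8 × ln(6/4.2) − 1.96) = Φ(1.10) = 0.865.
- Hazard scale: Φ((0.30 − 1.96/√77.5) / (0.70/√73.8)) = Φ(0.95) = 0.829.

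Over 1–5 per month these run from 88% down to 85% and from 84% down to 82%. Simulation with all 80 enrolled (20,000 trials) gives 0.877–0.856 for a one-sample log-rank test and 0.859–0.836 for an exponential test on the cube-root hazard scale. The 84% is sound as fixed-sample power. The cube-root test is the version closest to it.

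**Step 2: the plan's own tables.** If a stopped trial is not a success and the rules act independently:

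- Toxicity 20%: 0.84 × (1 − 0.0478) × (1 − 0.1346) = 0.84 × 0.9522 × 0.8654 = 0.69.
- Toxicity 30%: 0.84 × 0.9522 × 0.8324 = 0.67.

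**Step 3: joint simulation.** CR and toxicity boundaries recomputed from the stated beta priors match Tables 2 and 3 at every printed sample size. Simulated stopping at CR 20% was 0.136 and 0.169, against 0.1346 and 0.1676 in Table 4. The OS rule used the stated inverse-gamma priors, checked at each enrolment after the first 5 patients, with a cutoff of 0.025 chosen because it agrees with Table 1:

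| True median (months) | 2 | 3 | 4.2 | 5 | 6 | 7 |
|---|---|---|---|---|---|---|
| Simulated stopping | 1.00 | 0.895 | 0.252 | 0.110 | 0.047 | 0.025 |
| Table 1 | 0.9999 | 0.8882 | 0.2332 | 0.1088 | 0.0478 | 0.0236 |

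With all three rules at median 6, CR 20% and 3 per month (20,000 trials), some rule stopped 18.0% of trials at toxicity 20% and 21.2% at toxicity 30%. Mean enrolment was 68.0 and 66.2. OS power, toxicity 20% / 30%:

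| Test | All 80 enrolled | Stop = no success | Enrolled patients tested after a stop |
|---|---|---|---|
| Cube-root exponential | 0.842 | 0.699 / 0.672 | 0.717 / 0.697 |
| One-sample log-rank | 0.862 | 0.715 / 0.687 | 0.742 / 0.723 |

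Against each test's own fixed-sample power the loss is about 12–17 points. With the CR/toxicity rules alone, the cube-root test gives 0.730 / 0.702 (stop = no success) or 0.748 / 0.727 (still tested). Across both tests those rules account for about 9–14 points, and the OS rule for about 3 more.

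**Step 4: sensitivity.**

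- Accrual of 1–5 per month: 0.67–0.76 over both tests and both conventions.
- A different OS rule that also stops about 5% at median 6 (cutoff 0.05, first look after 15 patients): every figure within 0.3 points of the table.
- CR and OS positively correlated (assumed Gaussian copula, 0.3–0.7): 0.68–0.74.
- Toxicity as low as 5% (assumed): 0.71–0.75, because most of the loss comes from the CR rule.

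**The case against.** The sentence in section 11.0 is conditional on 80 patients and correct on that reading. The stopping probabilities are disclosed in Tables 1 and 4, so nothing is hidden. This stands, and it is why the remedy is to relabel 84% rather than withdraw it. Section 11.0 nevertheless gives no other power, and under the plan's own targets about one trial in five does not reach 80.

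The low end of the range counts every stop as a failure. Section 11.2 speaks of ceasing accrual, section 7.0 continues survival follow-up for up to 5 years, and Table 1's durations fit 12 months of follow-up even in stopped scenarios. That favours testing the enrolled patients, but section 11.1 also speaks of terminating the study and nothing settles the matter. Testing them raises power only to 70–74%.

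Response is first assessed by marrow after cycle 2 (section 7.0), so CR data lag accrual. With assumed lags of 2–3.25 months for CR and 1–1.5 months for toxicity, and enrolled patients tested, power is 0.71–0.75. The result also depends on the true CR rate: at CR 30% and toxicity 20% it is 0.78–0.80. CR 20% is, however, the plan's postulate.

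Finally, the OS cutoff used here is not the printed 0.05. Applied at every enrolment, 0.05 stops about 12–14% of trials at median 6, against 4.78% in Table 1, and takes power to roughly 61–70%. That mismatch is a separate issue; matching Table 1 favours the plan. None of these points restores 84%.

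**Conclusion.** The concern holds. The power of the design as monitored is not stated and is below 84%. At median OS 6 months, CR 20% and accrual of 3 per month, it is about 67–74%, or 67–76% over the stated accrual range. The range spans toxicity of 20–30%, two reasonable tests and both ways of counting a stopped trial.

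The direction is certain, since it follows from Tables 1 and 4 alone. The exact value depends on the OS rule behaving as Table 1 reports, on the test chosen, and on CR results being available without delay. Allowing correlation between CR and OS changes little. Much of the loss is deliberate stopping on CR or toxicity rather than a failed OS test, but the consequence for the OS objective is the same.

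Two smaller points barely affect power. Neither section 11.0 nor 11.3 names the test statistic. And 80 patients at 1 per month take 80/12 = 6.67 years, whereas 3.33 years corresponds to 2 per month.

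**What to change.** In section 11.0:

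- State OS power net of all three rules at median 6 months and CR 20%, with toxicity 20% and 30% as labelled scenarios. Give the accrual rate, the schedule of OS looks and how a stopped trial is counted. A result of about 67–75% should be expected. A row at CR 30% would show the sensitivity.
- Keep 84% only if it is labelled as fixed-sample power that applies when no rule stops the trial.
- Say whether the OS test is carried out on the enrolled patients after an early stop, and after how much follow-up.

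Minor edits: in section 11.3 name the test that matches section 11.0 (an exponential or one-sample log-rank test against a median of 4.2 months, two-sided 0.05) and quote the fixed-sample power for that test; reconcile 1–5 patients per month with the 3.33-year maximum.

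The cost is one joint simulation and a few sentences. The stated power becomes less favourable. No boundary, sample size or decision rule changes.

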11.1 Overall Survival Monitoring

The efficacy endpoint, OS, will be continuously monitored using the Bayesian method by Thall et al.³⁷ Let T_s and T_e represent the OS times for the historical regimen and the experimental regimen OM, respectively. We assume $T_s|M_s$ and $T_e|M_e$ follow an exponential distribution with respective median M_s and M_e . Furthermore, we assume that the prior for M_s follows an inverse gamma distribution $IG(5.0, 16.8)$ to reflect our knowledge of OS in patients treated historically with standard regimen. This prior distribution has a mean of 4.2 months, and a variance of 5.88. The prior for M_e is assumed to be $IG(2.18, 4.94)$, which has the same mean of 4.2 months and a larger variance of 100 to reflect our uncertainty about the median OS of the proposed experimental regimen, OM.

The OS will be continuously monitored, and the study will be terminated early if, based on the available data, there is less than 5% chance that the median OS in patients treated with OM will improve by more than 1.8 months, compared to the historical regimen. The futility stopping rule is as follows:

$$\Pr(\text{Me} > \text{Ms} + 1.8 \text{ months} \mid \text{data}) < 0.05$$

The operating characteristics of this decision rule are summarized in Table 1 using the one-arm TTE software developed by the Department of Biostatistics at M.D. Anderson Cancer Center.

Table 1. Operating characteristics for the design (based on 5000 simulations)

Scenario	True Median (months)	$\Pr(\text{Stopped Early})$	Mean No. patients	Average Trial Duration (months)
1	2.0	0.9999	13	16.26
2	3.0	0.8882	32	22.54
3	4.2	0.2332	66	34.00
4	5.0	0.1088	73	36.29
5	6.0	0.0478	77	37.58
6	7.0	0.0236	78	38.05

The monitoring for OS will be carried out through the Clinical Trial Conduct (CTC) website (<https://biostatistics.mdanderson.org/ClinicalTrialConduct>) which is housed on a secure server at MDACC and maintained by the MDACC Department of Biostatistics. Access to the website will be gained through usernames and passwords provided by the MDACC Department of Biostatistics. Training on the use of the CTC will be provided by the biostatistical collaborator of the study, with emphasis on the importance of timely updating of follow-up times and recording of events. The monitoring rule for OS will be applied continuously when a new patient is enrolled or an existing patient's data is updated. If the stopping rule is met, an automatic email will be sent out to the study PI, RN and the study statistician to keep them informed and the CTC website will not allow enrollment of any new patients.

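### As written, the OS futility rule can lock accrual on two or three early deaths, and at the target median it closes the trial about 12–17% of the time, not the 4.78% in Table 1

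*Combined protocol and SAP*

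**What the plan says.** Section 11.1 models OS as exponential and places inverse-gamma priors on the two medians. The historical median Ms has IG(5.0, 16.8): "This prior distribution has a mean of 4.2 months, and a variance of 5.88". The OM median Me has IG(2.18, 4.94), "which has the same mean of 4.2 months and a larger variance of 100 to reflect our uncertainty about the median OS".

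The trial stops for futility when "there is less than 5% chance that the median OS in patients treated with OM will improve by more than 1.8 months", that is, when Pr(Me > Ms + 1.8 | data) < 0.05. On timing, "The monitoring rule for OS will be applied continuously when a new patient is enrolled or an existing patient's data is updated". Once the rule is met, the monitoring website refuses new enrolments.

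Section 11.1 sets no minimum number of patients or deaths. The minimum of 5 patients in section 11.2 belongs to the CR and toxicity rules. Table 1 reports a 0.0478 probability of early stopping at a true median of 6.0 months, the target in section 11.0, and 0.2332 at 4.2 months.

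**The concern.** Equal means with a wider variance read like a vague, even-handed prior. At shape 2.18 an inverse gamma is strongly right-skewed: a long upper tail carries its mean and most of its mass lies lower. The rule works on probabilities, not on the mean. It therefore begins with OM more likely worse than better than the historical regimen, and with little prior weight to resist a few early deaths.

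With continuous looks and no minimum, two or three early deaths may be enough to block enrolment. If OM really has a 6-month median, that closure is an error, and it costs the trial the OS comparison on which its 80 patients are sized. Table 1 would lead a reader to think this risk is below 5%.

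**Working it through.** **1. Stated moments.** For IG(a, b), the mean is b/(a−1) and the variance is b²/[(a−1)²(a−2)].
- IG(5, 16.8): 16.8/4 = 4.2; 16.8²/(16 × 3) = 5.88.
- IG(2.18, 4.94): 4.94/1.18 = 4.19; 4.94²/(1.18² × 0.18) = 97.4. Unrounded parameters 2.1764 and 4.9409 give 4.2 and 100.

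The plan's figures reproduce to rounding.

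**2. What mean-matching implies.** The prior medians are 2.66 months for OM and 3.60 for the historical regimen. Numerical integration gives Pr(Me > Ms) = 0.364 and Pr(Me > Ms + 1.8) = 0.194. In the update below, the OM prior counts as 2.18 deaths in 4.94/ln 2 = 7.13 patient-months.

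**3. Stopping boundary at 0.05.** With exponential survival parameterised by its median, d deaths in T total patient-months give Me | data ~ IG(2.18 + d, 4.94 + T ln 2).
- 1 death, T = 0: probability 0.057, so one death cannot stop the trial.
- 2 deaths: stop if T < 3.58 (0.0489 at 3.5; 0.0502 at 3.6).
- 3 deaths: stop if T < 7.85.
- 4 deaths: stop if T < 12.30.

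T is summed over all patients.

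**4. The two-death path alone.** At a true 6-month median the hazard is ln 2/6 = 0.1155 per patient-month. Expected deaths in 3.58 patient-months are λ = 0.1155 × 3.58 = 0.4136. The chance that the second death falls inside that window is 1 − e^(−λ)(1 + λ) = 1 − 0.6613 × 1.4136 = 0.065. If the rule is evaluated when a death is recorded, this single path already exceeds Table 1's total of 0.0478.

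**5. Accrual assumption.** Section 11.0 gives 1–5 patients per month. Table 1's durations fit 3 per month plus 12 months: (34.00 − 12) × 3 = 66 patients and (37.58 − 12) × 3 = 76.7, against 66 and 77 in the table. I assume 3 per month.

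**6. Probability of early stopping** (10,000 simulated trials per scenario, looks at each enrolment, no minimum; mean patients in brackets):

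| True median | Table 1 | Written rule, 0.05 | Same prior, 0.025 |
|---|---|---|---|
| 2.0 | 0.9999 (13) | 1.000 (9) | 1.000 (12) |
| 3.0 | 0.8882 (32) | 0.966 (21) | 0.887 (31) |
| 4.2 | 0.2332 (66) | 0.450 (52) | 0.249 (65) |
| 5.0 | 0.1088 (73) | 0.234 (64) | 0.107 (73) |
| 6.0 | 0.0478 (77) | 0.125 (71) | 0.051 (76) |
| 7.0 | 0.0236 (78) | 0.083 (74) | 0.030 (78) |

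Table 1's simulation error at 6.0 months is √(0.0478 × 0.9522/5000) = 0.003, so 0.125 is not noise. At 0.05, monthly looks give 0.101 at 6.0 months and 0.406 at 4.2. Three-monthly looks give 0.060 and 0.319. A minimum of 5 or 10 patients with enrolment looks gives 0.118 or 0.082 at 6.0. None of these reproduces Table 1.

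**7. False closure at 6.0 months under the written rule.** It is about 12–13% with looks at enrolment only and 16–17% with looks at deaths as well. Most closures come within the first 10 patients (about 9% and 11–12% of all trials). Closures on 3 or fewer deaths are about 7–10% of all trials.

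**8. Dependence on the cutoff.** At 0.025 with the prior unchanged, the two-death boundary falls to 1.39 patient-months. False closure is 4.0% with monthly looks, about 5% at enrolments and about 7% with looks at deaths as well.

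**The case against.** Section 11.1 makes no false statement about the priors. The mean and variance are right, it nowhere claims equal medians or equipoise, and matching means is a disclosed choice. That stands; the criticism is of what the choice does in the rule.

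A reader might infer that the 19% starting probability itself shows a biased prior. It does not. Giving OM the identical historical prior IG(5, 16.8) would start at 22%, so most of the low value comes from the 1.8-month margin. The evidence for the tilt is Pr(Me > Ms) = 0.36 and the gap between the medians.

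A reader might also infer that the prior alone causes the early closures, so that any table computed from these priors would show them. The documents do not support that. With the same prior and a 0.025 cutoff, false closure is close to Table 1's figure. Prior weight, cutoff and the absence of a minimum all contribute, and much of the excess over 4.78% may be a mismatch between text and table. Which cutoff was intended cannot be known from the documents.

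Table 1 does not, however, dispose of the point. It does not describe the rule that the text states, and the text is what a reader would expect to be programmed.

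**Conclusion.** The point holds for the rule as written: IG(2.18, 4.94), cutoff 0.05, continuous looks, no minimum. The prior starts OM behind (0.36), and jointly with the margin, the light prior weight, the cutoff and the missing burn-in it lets 2 deaths in under 3.58 patient-months, or 3 in under 7.85, lock accrual. At a true 6-month median, false closure is about 12–17%, roughly three times Table 1's 4.78%. The boundaries follow exactly from the stated priors. The percentages rest on exponential survival, 3 patients per month and the look schedule. If the programmed cutoff is 0.025, the figure is about 4–7% and what remains is mainly a reporting matter.

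**What to change.** 1. **Reconcile first.** Check which cutoff the monitoring website uses, make the section 11.1 text and Table 1 agree, and rerun the operating characteristics for that rule, stating the look schedule, the accrual rate and any minimum.

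2. **If 0.05 stands, choose one:**
   - Match the medians with IG(2.18, 6.68). Pr(Me > Ms) becomes 0.50, Pr(Me > Ms + 1.8) becomes 0.30, the two-death boundary falls to 1.07 patient-months, and false closure at 6 months is about 6–9%. The text must then drop the shared mean: the prior mean becomes 6.68/1.18 = 5.66 months and the variance 6.68²/(1.18² × 0.18) = 178.
   - Keep the prior and begin OS monitoring after 10–15 patients. False closure is about 8–12% at 10 and 6–8% at 15, with closures on 3 or fewer deaths about 1% or less.

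3. **Report** the prior Pr(Me > Ms) and Pr(Me > Ms + 1.8) in section 11.1.

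Setting OM's prior median at 4.2 months with IG(2.18, 7.80) is tempting and lowers false closure further. It should not lead: its prior mean is 7.80/1.18 = 6.6 months, above the target, and it favours OM before any data (Pr(Me > Ms) = 0.57).

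**Cost.** One parameter or one minimum, in the text and on the website, plus a simulation rerun. Stopping at a true 4.2-month median falls from about 0.45–0.50 to about 0.37–0.41 with IG(2.18, 6.68), or 0.39–0.47 with the burn-in. Mean enrolment there rises from about 48–53 to 52–60, still below the 66 in Table 1.
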